6.3. Recruitment

Patients meeting inclusion/exclusion criteria and have an existing clinical encounter with a Cooper University Health Care neurological provider during the enrollment period will be offered enrollment. Recruitment will include explanation of the study using standardized language by a subinvestigator and written information about the study using simple language. The patient will have an opportunity to deny enrollment, proceed with providing consent, or opt for a follow-up phone outreach by a subinvestigator within 1-2 weeks. The purpose of the follow-up phone outreach is to provide a standardized approach for when the patient expresses that they need more time to make a decision regarding participation, and thus are deferring making a decision to consent or decline. The 2-week period will provide the opportunity for the patient to review the informed consent document and discuss their participation with other supportive individuals (i.e., family members, friends, primary care provider, etc.). This also provides the patient with an opportunity to deliberate any questions they may have. The follow-up phone outreach with physician study personnel is to a) address any questions that have arisen during the deliberation process and b) ascertain whether the patient has decided to consent to participate or not. No further advertising will be performed.

6.4. Screening

Upon enrollment, the neurological provider will be asked to verify past medical history (i.e., tobacco use, obesity status, past traumatic brain injury, diabetes mellitus, hypertension, hyperlipidemia) and current medications during the clinical encounter. Patients would undergo a pre-treatment serum metabolic blood panel to document baseline serum glucose levels, which is a routine biomarker to assess prior to administering glucocorticoid medications. Specific for research purposes only, patients would also be asked to score baseline MIDAS, 4-point verbal rating scale, and 11-point numeric pain scores (Appendix G). Patients will be instructed to keep a Study Diary, and will be instructed to record migraine episodes and any adverse events with date of onset, duration, and description for four weeks before and three months after treatment.

Patients with baseline serum glucose of above 400 mg/dL will fail screening procedures and not be included within the study due to elevated risk of acute exacerbation of steroid hyperglycemia during methylprednisolone administration.

7. STUDY TREATMENT, PROCEDURES, AND GUIDELINES

7.1. Study Intervention

After baseline screening assessment, patients will be scheduled within one month for investigational drug administration. Xylocaine®-MPF will be prepared for administration of 40 mg of active lidocaine hydrochloride per dose as described in Section 3.1.4. A total of two doses (40 mg lidocaine hydrochloride per dose; 80 mg total) of lidocaine hydrochloride will be prepared for the injection of each dose into each middle meningeal artery (left and right). SOLU-MEDROL® will be prepared for administration of 20 mg of active methylprednisolone sodium succinate as described in Section 3.1.4. A total of two doses (20 mg methylprednisolone sodium succinate per dose; 40 mg total) of methylprednisolone sodium succinate will be prepared for the injection of each dose into each middle meningeal artery (left and right). No placebo agents will be used during the study. Agents will not be blinded. Agents will be prepared and stored per instructions contained within Section 16 (HOW SUPPLIED/STORAGE AND HANDLING) of the Prescribing Information and manufactures' guidelines contained within the packaging insert.

The treatment will be administered in the Acute Stroke and NeuroInterventional Suite at Cooper University Health Care. The care team will include an experienced neurointerventional physician with extensive experience in proper catheter placement and technical specifications necessary for the procedure below, certified and licensed angiography technicians, a dedicated anesthesiology care team, pharmacy team, and nursing team comprised of neurocritical care certified nurses (including post-procedural recovery and observation). Within the immediate treatment area, availability to resuscitative equipment and continuous vital sign monitoring, including rapid cycling continuous blood pressure monitoring (with measurements at least every 5 minutes), continuous pulse oximetry, respiratory rate, continuous heart rate monitor, and electrocardiographic monitoring, will be ensured. For safety, patients may be sedated using institutional monitored anesthesia care (MAC) protocol under the care of a licensed anesthesiologist, and thus will not require intubation. Patients will be monitored continuously throughout the procedure and for four hours post-operatively in a dedicated post-angiography care unit.

The following steps will be performed interprocedurally:

- 1. Intra-arterial access will be obtained under ultrasound guidance via femoral or radial artery.
- 2. Fluoroscopic-guided catheterization and intracranial vascular access to the middle meningeal artery will be obtained using devices per neurointerventional provider discretion.
- 3. Manual infusion of 40 mg lidocaine bolus will occur over 5 minutes.
- 4. The provider will wait 2 minutes before administering active medications to assess for toxicity or acute adverse reactions.
- 5. Manual infusion of 20 mg methylprednisolone bolus will occur over 5 minutes.
- 6. The provider will wait at least 5 minutes before administering active medications to the contralateral side to assess for toxicity or acute adverse reactions.
- 7. The intravascular access will be retracted from intracranial circulation and navigated to the contralateral middle meningeal artery.
- 8. As described in Steps 3-5, infusion of lidocaine and methylprednisolone will occur.
- 9. Intravascular catheters will be retracted and access site will be sealed with appropriate closure device.

The following intra-procedural protocol adjustment is allowed: in the event of concern for overdose or other toxicity, the protocol permits administering half-strength dosages prior to completing administration of full dosage amounts (for example, administering 20 mg of lidocaine over the 2-5 min, waiting 2 minutes, and then subsequently administering the remaining 20 mg of lidocaine over another 2-5 min interval to result in a complete administration of a full dose). If this protocol adjustment is enacted, the Investigator must document this variation from standard protocol in procedural documentation.

Following study drug administration, patient will be monitored for post-procedure recovery by a nursing staff member for at least 4 hours. During this time, the patient's vital signs will be monitored, including continuous electrocardiogram, pulse oximetry, cyclic blood pressure monitoring (with measurements obtained at least every 15 minutes), respiratory rate, and heart rate monitoring. The catheterization access site will be assessed 2 hours following administration to ensure adequate closure and absence of access site hematoma.

7.2. Study Assessment and Activities

Summary of all study-related visits and activities are described in Table 1, including screening procedures and study drug administration.

	Visit 1 (Screening)	Visit 2 (Administration) (Week 0) ^a	Visit 3 (Week 1) ^b	Visit 4 (Week 6) ^b	Visit 5 (Week 12) ^b
Informed Consent	Х				
Medical History	Х				
Concomitant Medication Review	Х	Х	Х	Х	Х
Complete Neurological Physical Exam	Х	Х	Х	Х	Х
Vital Signs	Х	Х	Х	Х	Х
Comprehensive Metabolic Blood Panel	Х	Х			
Pregnancy Test (Urine or Serum)	Х				
MIDAS Score (Appendix A)	Х	Х	Х	Х	Х
4-point Verbal Rating Scale (Appendix B)	Х	Х	Х	Х	Х
11-point Numeric Pain Rating Scale (Appendix C)	X	X	X	X	X
Subject Diary Review	X	Х	Х	Х	X
Study Drug Administration		Х			

Table 1. Schedule of Study Visits

^aApproximately 4 weeks of Visit 1

^b± 2 days

7.2.1. Visit 1 (Screening)

- 1. Review the study with the subject and obtain written informed consent and HIPAA authorization.
- 2. Assign the subject a unique screening number.
- 3. Record demographics data.
- 4. Record medical history, including history of tobacco use, obesity status, past traumatic brain injury, diabetes mellitus, hypertension, hyperlipidemia, migraines), diagnosis date, and prior preventative medications trialed for migraine treatment.
- 5. Record current, concomitant medications.
- 6. Perform a complete neurological physical exam, including visual field assessment, fundoscopic exam, cranial nerve exam, peripheral motor and sensory fields, and reflexes.
- 7. Perform and record vital signs, including blood pressure monitoring.
- 8. Perform clinical laboratory tests (i.e., complete metabolic blood panel and pregnancy test as applicable).
- 9. Administer migraine-related symptom scores (i.e., MIDAS, 4-point Verbal Rating Scale, 11-point Numeric Pain Rating Scale).
- 10. Initiate Subject Diary, including instructions to record migraine episodes and any adverse events with date of onset, duration, and description.
- 11. Schedule subject for Visit 2 (study drug administration).

7.2.2. Visit 2 (Administration)

(Week 0 – Approximately 4 weeks after Visit 1).

- 1. Record any changes to concomitant medications.
- 2. Perform a complete neurological physical exam, including visual field assessment, fundoscopic exam, cranial nerve exam, peripheral motor and sensory fields, and reflexes.
- 3. Perform and record vital signs, including blood pressure monitoring.
- 4. Administer study drug (lidocaine hydrochloride and methylprednisolone serially).
- 5. Perform clinical laboratory tests (i.e., complete metabolic blood panel) following study drug administration.
- 6. Administer migraine-related symptom scores (i.e., MIDAS, 4-point Verbal Rating Scale, 11-point Numeric Pain Rating Scale).
- 7. Review Subject Diary, including details of any migraine episodes.
- 8. Schedule subject for Visit 3.

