3.4. Risk / Benefit Assessment

Risks associated with intra-arterial administration route includes rare adverse events related to intravascular access, including allergic response to contrast agents, vessel injury, access site hematoma, and infection. Risks will be mitigated by implementation of institutional standard practices protocol, including standardized procedures in the event of an interventional accessrelated complication.

For example:

- Protocols are in place to obtain an ultrasound study if access site hematoma is suspected post-administration of the study drug.
- In case of unexpected, severe contrast allergy, a combination of intravenous fluids, diphenhydramine, hydrocortisone, and/or adrenaline will be administered.

Risks associated with sedative mediations used for "twilight anesthesia"/monitored anesthesia care (MAC) include the risk of excessive or prolonged sedation, potentially requiring intubation. Risks will be mitigated by using minimal sedation necessary to safely obtain interventional access.

Risks associated with methylprednisolone administration include teratogenic effect on unborn fetuses. Risks will be mitigated by pre-treatment urine pregnancy test to screen for pregnancy in patients of child-bearing age.

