No specific methylprednisolone-related risks are anticipated for the investigational dosing amount and route. The following are potential complications for methylprednisolone use per Section 5 (WARNINGS AND PRECAUTIONS) for the Prescription Drug Labeling of NDA 011856. Complications with methylprednisolone treatment are dependent on dosage size, duration, and route of administration. Methylprednisolone has been associated with rare serious neurological adverse events, including spinal cord infarction, paraplegia, quadriplegia, cortical blindness, and stroke, with epidural administration. There have been rare reports of anaphylactoid reactions. Large doses of corticosteroids have been associated with elevated blood pressure and increased potassium and calcium excretion. After recent myocardial infarction, there has been a suggested association between drugs within the corticosteroid pharmacologic class and left ventricular free wall rupture. Chronic methylprednisolone use is associated with hypothalamic-pituitary adrenal axis suppression, Cushing's syndrome, and hypoglycemia. High doses of cyclic, pulsed methylprednisolone administration are associated with toxic acute hepatitis. Corticosteroid use is associated with increased susceptibility to infections, including fungal infections.

Other risks of participation include very rare adverse events related to route of administration, including allergic response to agents, vessel injury, access site hematoma, and infection.

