6.2. Exclusion Criteria

- 1. Pregnant, breastfeeding, or unwilling to practice contraception during participation in the study. Medically acceptable contraceptives include: (1) surgical sterilization (such as a tubal ligation or hysterectomy), (2) approved hormonal contraceptives (such as birth control pills, patches, implants or injections), (3) barrier methods (such as a condom or diaphragm) used with a spermicide, or (4) an intrauterine device (IUD).
- 2. Presence of a condition or abnormality that in the opinion of the Investigator would compromise the safety of the patient or the quality of the data.
- 3. Patients with concomitant intracranial pathology (e.g., intracranial malignancy).
- 4. Blood glucose level on screening complete metabolic blood panel > 400 mg/dL.
- 5. Patients with known hypersensitivity and/or contraindication to either lidocaine hydrochloride or methylprednisolone sodium succinate, including:
 - Patients with known history of hypersensitivity to local anesthetics of the amide type.
 - Patients with systemic fungal infections.
 - Patients with known or suspected hypersensitivity to cow's milk or its components or other dairy products (SOLU-MEDROL® 40mg presentation includes lactose monohydrate, and may contain trace amounts of milk ingredients).
- 6. Patients taking chronic medications that, when co-administered with lidocaine and other local anesthetics, are at increased risk of developing methemoglobinemia: nitrates/nitrites, local anesthetics, antineoplastic agents, antibiotics, antimalarials, anticonvulsants, acetaminophen, metoclopramide, quinine, sulfasalazine.
- 7. Patients taking chronic medications that, when co-administered with methylprednisolone, are at increased risk for hypokalemia, altered drug levels, convulsions, or altered clearance: amphotericin B, diuretics, aminoglutethimide, macrolide antibiotics, anticholinesterases, antitubercular drugs, cholestyramine, cyclosporine, digitalis glycosides, estrogens (including oral contraceptives), hepatic enzyme inducers/inhibitors, and ketoconazole.
- 8. Patients have known contraindications for angiography. Patients with contrast allergy will be premedicated with diphenhydramine and steroids.
- 9. Patient has known active systemic infection or sepsis.
- 10. Patient has contraindication to anesthetic agents used for conscious sedation/monitored anesthesia care (MAC).
- 11. Concurrent participation in another research protocol for investigation of an experimental therapy.

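### The only scheduled pregnancy test is at Visit 1, about 4 weeks before dosing; no Visit 2 step tests for pregnancy before study drug is given

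*Combined protocol and SAP*

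**What the plan says.** All references are to the combined protocol and SAP.

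- **Risk and mitigation.** Section 3.4 lists a teratogenic effect among the risks of methylprednisolone and answers it with a test: "Risks will be mitigated by pre-treatment urine pregnancy test to screen for pregnancy in patients of child-bearing age". It does not say how close to dosing the test must be.
- **Schedule.** In Table 1 (Section 7.2) the row "Pregnancy Test (Urine or Serum)" has one mark, in the Visit 1 column. Visit 1 step 8 agrees: "Perform clinical laboratory tests (i.e., complete metabolic blood panel and pregnancy test as applicable)".
- **Dosing visit.** Section 7.2.2 places Visit 2 "Approximately 4 weeks after Visit 1". Its only laboratory step reads "Perform clinical laboratory tests (i.e., complete metabolic blood panel) following study drug administration".
- **Eligibility.** Exclusion 1 in Section 6.2 rules out anyone "Pregnant, breastfeeding, or unwilling to practice contraception during participation in the study".
- **Qualifying text.** Section 3.4.1 states "No specific methylprednisolone-related risks are anticipated for the investigational dosing amount and route". For the risks of vascular access, Section 3.4 says "Risks will be mitigated by implementation of institutional standard practices protocol", but the content of that institutional protocol is not shown.

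**The concern.** A pregnancy test describes the patient on the day it is done. At dosing this one is about 4 weeks old, so it cannot show that the patient still meets the pregnancy exclusion, or that the risk named in Section 3.4 is controlled at the time of exposure. Two kinds of pregnancy pass through: a conception shortly before Visit 1, too early for that test to detect, and a conception between the two visits.

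At stake is an avoidable fetal exposure. The protocol counts a congenital anomaly as a serious adverse event (Section 8.1), and serious adverse events are among the primary safety endpoints (Section 4.1). Collection of serious adverse events ends with the final visit at Week 12, and a birth after exposure in early pregnancy would ordinarily come later than that. Prevention before dosing is therefore the main control available.

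**Working it through.** The plan gives no figure of its own here, so the check sets the texts side by side and then expresses the gap in days.

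**1. Where the test is scheduled**

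| Place | Pregnancy test? |
|---|---|
| Table 1, Visit 1 | Yes |
| Table 1, Visits 2 to 5 | No |
| Section 7.2.1, step 8 | Yes, where applicable |
| Section 7.2.2, steps 1 to 8 | No |
| Section 7.1, narrative and nine procedural steps | No |

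The eight Visit 2 steps are: medication changes, neurological examination, vital signs, study drug, metabolic panel after study drug, symptom scores, diary review, and booking Visit 3. None is a pregnancy test, and only the first three precede dosing. The test thus appears at 1 of 5 visits.

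**2. The gap between test and dosing, G**

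Section 7.2.2 gives about 4 weeks, so G = 28 days. Section 7.1 says only that dosing is scheduled within one month of screening, which would allow a shorter gap. Section 6.4, however, asks for a diary covering the four weeks before treatment, and the diary starts at Visit 1. About 28 days is therefore the designed interval.

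**3. The detection lag, L**

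The documents give none. I assume a test turns positive L = 7 to 14 days after conception.

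**4. Window of conceptions, counted back from dosing, that scheduled testing would miss**

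- Visit 1 test only: G + L = 28 + 7 = 35 days, or 28 + 14 = 42 days.
- With a test at Visit 2: L = 7 days, or 14 days.
- Difference: (G + L) − L = G = 28 days in either case.

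**5. How those 28 days divide**

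| | L = 7 | L = 14 |
|---|---|---|
| Before Visit 1 (L days) | 7 (7/28 = 25%) | 14 (14/28 = 50%) |
| Between the visits (G − L days) | 21 (21/28 = 75%) | 14 (14/28 = 50%) |

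The contraception requirement applies during participation. It can reduce conceptions in the second row but does not reach back to the first. Nor is it re-checked at Visit 2: the medication review would show a changed hormonal method, but not a lapse in a barrier method.

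The percentages are shares of calendar days, not of risk. The calculation also assumes the pregnancy has not been recognised in some other way.

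**The case against.** The strongest reply is that nothing in the plan is breached. Section 3.4 promises a test before treatment, a Visit 1 test is before treatment, and no section sets a maximum interval. That is correct: the weakness is one of timing, not a contradiction.

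Several further points bear on weight:

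- **Small exposure.** At most 10 patients are treated, an unknown number of whom can conceive. Each has one session, with 2 × 20 mg = 40 mg methylprednisolone in total, and Section 3.4.1 anticipates no specific methylprednisolone-related risk at this dose and route. This stands, and it is why the point is a recommended improvement and not a critical flaw.
- **The day count.** The days gained equal the visit interval by construction, and a shorter interval reduces them one for one. Both statements are true. The count shows which conceptions are missed and makes no claim about how likely they are.
- **Recognition by other means.** Conceptions before Visit 1 are the oldest at dosing, and so the most likely to have been noticed by the patient. This is fair, but the protocol does not ask about it at Visit 2.
- **Contraception.** Sterilisation, an intrauterine device or an implant will often predate Visit 1, so for some patients the earlier window is covered in practice. Against that, exclusion 7 rules out chronic estrogen use, including oral contraceptives, although exclusion 1 accepts birth control pills. Some patients may therefore have to rely on other methods, including barrier methods.
- **Institutional practice.** The access and monitored anesthesia care protocols may already include a same-day test. They are cited but not shown, and the trial documents state no such test. What is certain is the omission from the written schedule, not that no check would take place.
- **Scope of the remedy.** The protocol names a fetal risk for methylprednisolone only, and none for radiation. Placing the test before sedation and fluoroscopy is a matter of sensible order: it avoids starting a procedure that would then have to stop.

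**Conclusion.** The concern holds. As written, the schedule allows study drug to be given in an early pregnancy that a test on the day would have found, although Section 3.4 relies on a pregnancy test for exactly this risk.

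The size can be stated only as time: the window missed by scheduled testing is 35 to 42 days now and would be 7 to 14 days with a Visit 2 test. This rests on the 28-day interval and the assumed lag of 7 to 14 days. No probability can be given, because the documents contain neither a conception rate nor the number of participants able to conceive. The absolute risk is small. The change is still worth making, because the procedure is scheduled in advance and can be deferred.

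**What to change.** 1. In Table 1, mark the pregnancy test at Visit 2 for patients of child-bearing potential.
2. In Section 7.2.2, add a step ahead of the present step 4: urine pregnancy test, with a negative result required before sedation, fluoroscopy and study drug.
3. At the same step, confirm that contraception has continued since Visit 1.
4. If institutional practice already includes a same-day test, state it in these two places.

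The cost is one inexpensive urine test per applicable patient, at an existing visit, in a trial of up to 10, and a deferred procedure if the result is positive. Endpoints, analysis and sample size are unaffected. The change narrows the gap without closing it: under the assumed lag, a conception in the last 7 to 14 days before dosing can still be missed.

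### The 400 mg/dL glucose limit is tested only at screening, about 4 weeks before dosing; the one dosing-day panel is drawn after the drug, so a rise above the limit would be missed before dosing

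*Combined protocol and SAP*

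**What the plan says.** - **The limit.** Section 6.2, item 4 excludes on "Blood glucose level on screening complete metabolic blood panel > 400 mg/dL".
- **Its reason.** Section 6.4 says that patients above the limit will "not be included within the study due to elevated risk of acute exacerbation of steroid hyperglycemia during methylprednisolone administration".
- **When it is tested.** Section 7.2.1, item 8 lists the Visit 1 laboratory tests as "complete metabolic blood panel and pregnancy test as applicable".
- **The gap to dosing.** Section 7.1 says "patients will be scheduled within one month for investigational drug administration". Section 7.2.2 places Visit 2 "Approximately 4 weeks after Visit 1".
- **The order of steps at Visit 2 (Section 7.2.2).** Item 1 is "Record any changes to concomitant medications". Items 2 and 3 are the neurological examination and vital signs. Item 4 is dosing. Item 5 is "Perform clinical laboratory tests (i.e., complete metabolic blood panel) following study drug administration".
- **The schedule.** Table 1 marks the metabolic panel at Visits 1 and 2 only, without saying which side of dosing the Visit 2 panel falls on.
- **Discretion.** Section 6.2, item 2 also excludes for "Presence of a condition or abnormality that in the opinion of the Investigator would compromise the safety of the patient".
- **Patients in whom glucose may move.** Diabetes is recorded (Sections 6.4 and 7.2.1) but is not an exclusion. Section 6.2, item 8 allows patients with contrast allergy to enter with steroid and antihistamine premedication.

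**The concern.** The sponsor set a glucose threshold and said which risk it guards against. That risk arises when the steroid is injected, but the threshold is applied to blood drawn about 4 weeks earlier. Glucose can change over that time, for example in a patient with diabetes. It can also change in a patient given premedication steroid for the procedure, which the Visit 1 panel would not normally reflect.

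Patient safety is the main stake, in a trial whose primary outcome is safety. A second, smaller issue is interpretation. Clinically significant laboratory abnormalities are graded as adverse events (Section 8.1), and the incidence of events attributed to study drug is one of the primary endpoints (Section 4.1). A high post-dose glucose has no same-day pre-dose value to be read against, which somewhat weakens its attribution.

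**Working it through.** The plan states no figure to reproduce. The check is a reading of every scheduled glucose or metabolic panel against the time of dosing, followed by a count.

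**Timeline**

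| Time | Event | Source | Glucose measured? |
|---|---|---|---|
| About week -4 | Visit 1: panel drawn, limit applied | 6.2 item 4; 6.4; 7.2.1 item 8 | Yes |
| Week 0, before drug | Medication review, neurological examination, vital signs | 7.2.2 items 1-3 | No |
| Week 0 | Drug given to both sides | 7.2.2 item 4; 7.1 | No |
| Week 0, after drug | Panel drawn | 7.2.2 item 5 | Yes |
| Weeks 1, 6 and 12 | Follow-up visits | Table 1; 7.2.3-7.2.5 | No |

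**Could another reading close the gap?**

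- Section 6.4 speaks of a pre-treatment panel, but under the Screening heading and as the baseline value. It is the Visit 1 panel.
- Table 1 alone would allow a pre-dose draw at Visit 2, but Section 7.2.2, item 5 places that panel after the drug.
- The monitoring in Section 7.1 covers blood pressure, oximetry, respiratory rate, heart rate and electrocardiogram, both during the procedure and for at least 4 hours afterwards. Glucose is not listed.
- The gap of about 4 weeks is the intended one, because Section 6.4 asks for four weeks of diary before treatment.

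**Counts, with n = 10 (Section 5.3)**

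- Panels scheduled now: 2 x 10 = 20 (10 at screening, 10 after the drug).
- Same-day pre-dose glucose values now: 0 x 10 = 0.
- Methylprednisolone already given when the dosing-day panel is drawn: 2 x 20 mg = 40 mg, the full dose.
- Glucose values with one pre-dose test added: 3 x 10 = 30. Patients with a same-day pre-dose value rise from 0 of 10 to 10 of 10.

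These counts describe coverage and do not measure risk. The risk depends on the probability that a patient at or below 400 mg/dL at screening is above it at dosing, and on the added harm from 40 mg of methylprednisolone. The documents give neither, and I offer no estimate.

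**Attribution.** All-event and serious-event incidence do not depend on relatedness, so they are unaffected. For drug-attributed events, one patient misclassified in 10 moves the incidence by 1/10 = 10 percentage points. Table 3 in Section 8.1 reserves the unrelated category for events where this is certain, a standard that is hard to meet without a same-day pre-dose value.

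**The case against.** The best counter-argument is that a once-only laboratory criterion at screening is a legitimate choice, and Section 6.2 words it openly as one. The limit is high, the steroid is a single modest dose, and other safeguards are present: investigator discretion, the Visit 2 medication review, an anesthesiology team and at least 4 hours of observation. Institutional or anesthesia practice may include a glucose check that the protocol does not mention. The premedication example rests on no stated drug, dose or timing. Relatedness is judged on temporal sequence, response pattern and other causes, and the screening panel already gives a reference value. The pregnancy test is likewise done only at Visit 1, so glucose may be one case of a general scheduling remark.

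Much of this stands. The probability is probably low, and the attribution argument is secondary. Non-detection can be asserted only for the protocol's own procedures. The counts also assume 10 patients: Section 9.2 describes 10 as 50%, which would imply 10 / 0.5 = 20 and double them.

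It does not remove the point. None of the listed safeguards is a required glucose measurement, and unseen local practice cannot be relied on. The post-dose panel may show a high value, but only after the steroid has been given. The pregnancy-test timing is a separate matter and does not make the glucose gap acceptable.

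**Conclusion.** The concern holds. The protocol applies its own glucose limit only about 4 weeks before the exposure the limit is meant to make safer, and requires no glucose test on the dosing day until all 40 mg of methylprednisolone has been given. On the planned 10 patients, none has a protocol-specified same-day pre-dose value.

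This is a design choice that should be improved; it is not an internal contradiction. The safety consequence is probably infrequent but cannot be quantified from the documents. The effect on endpoints is limited to somewhat weaker attribution of a post-dose glucose abnormality. The conclusion assumes that the Section 7.2.2 steps are carried out in the order listed and that no unstated local procedure supplies the missing test.

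**What to change.** In Section 7.2.2 and Table 1, add a glucose test (point-of-care or metabolic panel) at Visit 2, taken before arterial access and after any steroid premedication, with the result in hand before dosing. Apply the existing 400 mg/dL limit to it, and defer dosing if it is exceeded. Extend Section 6.2, item 4 to match. Keep the post-dose panel and use the pre-dose value as its same-day reference.

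The cost is one extra routine test per patient (at most 10 at the Section 5.3 sample size), a short wait for the result and an occasional deferral. The test cannot fully separate a continuing effect of premedication steroid from that of the study methylprednisolone.
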